#### ***The noninflammatory diarrhea is defined if***

- 1) negative for *C. difficile* toxin and
- 2) no WBC on stool examination and
- 3) dramatic and persistent response to diet adjustment

Or

- 4) no mucosal inflammation or ulceration if colonoscopy is performed

The management and enrollment flow chart is shown in Figure 1.

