## **Study Protocol with Statistical Analysis Plan**

### **Background/Rationale**

Nosocomial diarrhea is defined as diarrhea that develops after 72 hours of hospitalization. This condition is common among hospitalized patients with reported prevalence of 14-21%. The causes of nosocomial diarrhea can be categorized into inflammatory and non-inflammatory causes. For inflammatory etiologies, the most concern is *Clostridium difficile* infection. Other infections such as cytomegaloviral enterocolitis can also occur because immune function can be suppressed during critical illness. Ischemic enterocolitis is another cause in the inflammatory group. The non-inflammatory causes include adverse effects of medications and tube-feeding diarrhea. Differentiating inflammatory diarrhea from non-inflammatory diarrhea is important. Investigations for distinguishing these two conditions are stool *C. difficile* toxin test and stool examination. Because the reported sensitivity of only 60-70% for *C. difficile* toxin test by EIA method, which is most widely used in many centers, and the diagnosis of CMV is based on pathological findings, inflammatory diarrhea cannot be excluded completely by the negative stool tests. Colonoscopy is still required in some cases. However, although colonoscopy is a low risk procedure, the risk may increase if performed in hospitalized patients, who may have many comorbidities. A noninvasive test that can better differentiate inflammatory from noninflammatory diarrhea could help physicians to perform colonoscopy more appropriately. Calprotectin is a protein found in human neutrophils, and it is released during active periods of inflammation of intestine. The sensitivity and specificity has been reported at 93% and 96%, respectively in differentiating inflammatory bowel disease from irritable bowel syndrome in outpatient setting. Hence, its benefit in differentiating inflammatory from noninflammatory diarrhea in nosocomial diarrhea is possible, but never been studied. In the present study, we aim

to study the efficacy of fecal calprotectin in distinguishing inflammatory nosocomial diarrhea from non-inflammatory nosocomial diarrhea. Furthermore, the level of fecal calprotectin has been reported to be associated with the degree of intestinal inflammation. It could have a role in determine prognosis of the patients.

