#### ***The inflammatory diarrhea is defined if***

- 1) positive for *C. difficile* toxin or
- 2) stool WBC more than 5/HPF or
- 3) inflammatory mucosa or ulceration noted on colonoscopy

[figure not shown]

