## Data collection process

All patients are required to consent to the study. Their stool samples will be routinely sent for microscopic examination (cell count and parasites) and *C. difficile* toxin. Fecal calprotectin will be kept at -80 celsius degree and will be measured for fecal calprotectin at the end of study. The patients baseline characteristics, indication of hospitalization, treatment, and clinical progression will be obtained. All patients will be managed by primary physicians who do not know the results of fecal calprotectin level.

This protocol has been approved by Siriraj Institutional Review Board on January 24, 2019. The approval number is 718/2561(EC4).

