## Outcome Measures

Primary outcome: To determine the efficacy of fecal calprotectin in distinguishing inflammatory nosocomial diarrhea from non-inflammatory nosocomial diarrhea.

Secondary outcome: Correlation of fecal calprotectin levels and prognosis of hospitalized patients with nosocomial diarrhea.

The participants with nosocomial diarrhea were tested for C.difficile and stool examination or further colonoscopy for definite diagnosis group of diarrhea. Their leftover specimens will be kept until the end of the study. Then all collected stool specimens will be measured for calprotectin levels. Overall data collected of 147 participants will be completed analyzed about August 2020.

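### The reference standard for the primary ROC leaves some toxin-negative patients without a label and, as printed, lets others meet both definitions

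*Combined protocol and SAP*

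**What the plan says.** The primary outcome (Outcome Measures) is how well fecal calprotectin separates inflammatory from non-inflammatory nosocomial diarrhea. Statistical Analyses assigns this to a ROC curve and a best cut-off, so the two definitions under Study procedures are the reference standard.

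- **Inflammatory:** any one of three criteria is enough: a positive toxin test, "stool WBC more than 5/HPF or" inflamed or ulcerated mucosa on colonoscopy.
- **Non-inflammatory:** criteria 1 to 3 are joined by *and*: a negative toxin test, "no WBC on stool examination and" a marked and lasting response to diet change. A separate line reading *Or* introduces criterion 4: "no mucosal inflammation or ulceration if colonoscopy is performed".

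On who has a colonoscopy, Background/Rationale says "Colonoscopy is still required in some cases". Outcome Measures describes toxin testing and stool examination "or further colonoscopy for definite diagnosis group of diarrhea". Data collection process says "All patients will be managed by primary physicians who do not know the results of fecal calprotectin level". Limitations and Caveats excludes patients who cannot have a colonoscopy because of procedural risk. Study procedures recruits patients on having been tested, not on being classifiable. It adds "The management and enrollment flow chart is shown in Figure 1", but that figure is not visible in the text reviewed.

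**The concern.** The two definitions are not complements. One cuts stool WBC at more than 5/HPF and the other at none, so a count of 1-5/HPF satisfies neither on its own. The diet criterion opens a second gap, for toxin-negative patients with no stool WBC who do not respond to diet and are not scoped. In the other direction, criterion 4 as printed stands alone, so a normal colonoscopy can make a patient non-inflammatory even when a stool test has already made that patient inflammatory.

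A patient with no label must be dropped or assigned by discretion, and a patient with two labels needs a precedence rule. Where the text gives neither, two analysts could obtain different groups, ROC curves and cut-offs from the same data. The choice is not neutral: dropping indeterminate patients can leave a clearer-cut case mix and make calprotectin look more accurate than it would be among the patients for whom the test is meant.

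**Working it through.** The plan gives no figure to reproduce here, so the check is one of logic.

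**Inputs (from the two definitions).** Toxin (positive, negative) x stool WBC (0, 1-5, above 5/HPF) x colonoscopy (none, normal, inflamed) x diet response (yes, no) = 2 x 3 x 3 x 2 = 36 profiles.

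**Step 1: inflammatory.** Toxin-positive: 18. Toxin-negative with WBC above 5: 6. Toxin-negative with WBC 0 or 1-5 and inflamed mucosa: 4. Total 18 + 6 + 4 = 28.

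**Step 2: the remainder.** 36 - 28 = 8 profiles, all toxin-negative with WBC 0 or 1-5 and colonoscopy absent or normal (2 x 2 x 2, counting diet response). Any of these that does not meet the non-inflammatory definition has no label.

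**Step 3: apply the non-inflammatory definition.** Its grouping is ambiguous, so several groupings were tried, each requiring that a colonoscopy was done before criterion 4 can be met.

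| Grouping of criteria 1-4 | Non-inflammatory among the 8 | No label | Both labels |
|---|---|---|---|
| A, as printed: (1 and 2 and 3) or 4 | 5 | 3 | 9 |
| B, 4 replaces only 3: 1 and 2 and (3 or 4) | 3 | 5 | 1 |
| C, 1 always required: 1 and ((2 and 3) or 4) | 5 | 3 | 3 |
| D, 1 and 2 and 3, plus 4 if scoped | 2 | 6 | 0 |
| Sequence: positive stool test decides, then colonoscopy, then criteria 1-3 | 5 | 3 | 0 |

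**Step 4: which profiles have no label.** Three are common to every row, all toxin-negative and without colonoscopy:

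- WBC 1-5/HPF with a diet response;
- WBC 1-5/HPF without a diet response;
- WBC 0 without a diet response.

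Under B and D, toxin-negative patients with WBC 1-5/HPF and a normal colonoscopy also have no label (2 profiles). D adds one more: WBC 0, no diet response, normal colonoscopy.

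**Step 5: which profiles have both labels.** As printed: toxin-positive with a normal colonoscopy (6 profiles); toxin-negative, WBC above 5/HPF, normal colonoscopy (2); toxin-negative, WBC 0, diet responder, inflamed mucosa (1). Total 6 + 2 + 1 = 9.

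**Step 6: a softer reading of the WBC condition.** If no WBC is taken to mean 5/HPF or fewer, groupings A to D leave 2, 2, 2 and 4 profiles without a label. Toxin-negative diet non-responders without colonoscopy remain unlabelled in all four.

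**The case against.** **Criterion 4 could count as met when no colonoscopy is done.** This is the best answer to the gap, and it shows that the gap does not exist under literally every reading. If criterion 4 also stands alone, no profile is unlabelled but 17 meet both definitions; a stool-tests-first order would then remove those overlaps too. If criterion 4 replaces only criterion 3, 4 profiles stay unlabelled, falling to 0 only if no WBC is also read as 5/HPF or fewer. The reading is strained. It makes the diet criterion needless for patients without colonoscopy, and it sits badly with Limitations and Caveats, which treats colonoscopy as the route to a definite diagnosis. The claim is therefore limited to groupings in which criterion 4 needs a performed colonoscopy.

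**Limitations and Caveats already deals with these patients.** Partly. It removes those who cannot be scoped because of risk. If it were meant to remove every unscoped patient without a label, none would remain under A or C. It does not say that, it does not cover WBC 1-5/HPF with a normal colonoscopy under B or D, and it does not resolve double labels. That some patients go unscoped for other reasons is an inference from passages that do not address the question directly.

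**Figure 1 may settle it.** It may show the order of tests, who goes on to colonoscopy and who is enrolled. A reader might infer from the visible text that no study rule requires a colonoscopy; without the figure that cannot be known.

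**The overlaps may be mostly theoretical.** Background/Rationale and Outcome Measures suggest stool tests first, which would remove them. A diet responder who is then scoped and found inflamed is a logical profile that no section describes. This objection largely stands; what remains is that the visible definitions state no order.

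**Conclusion.** In the readable text the reference standard for the primary ROC is not exhaustive and, as printed, not mutually exclusive. This is worth fixing, with moderate confidence. The gap is the firmer half: three profiles, forming two kinds of patient, under every grouping in which criterion 4 needs a performed colonoscopy. The double label depends on reading criterion 4 as standing alone and on no order of tests being set. Both halves are conditional on Figure 1.

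Profile counts carry no frequencies, so they do not show how many patients are affected or how far the AUC or cut-off would move. A reader might try to bound the number from the sample size of 61 per group and the statement "Overall data collected of 147 participants will be completed analyzed about August 2020": 147 - 2 x 61 = 25, or 17.0% of 147. The documents do not support that use. They do not say whether 147 is counted before or after unclassifiable patients are removed, and the difference says nothing about how many have no label. Nor do they show that the reported AUC will be inflated, only that excluding indeterminate patients can have that effect.

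**What to change.** Reconcile the two definitions, Limitations and Caveats and Figure 1 into one research classification rule, fixed before calprotectin is measured:

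1. Any inflammatory criterion makes the patient inflammatory.
2. A patient is non-inflammatory only if no inflammatory criterion is met and the non-inflammatory definition is satisfied, stating whether criterion 4 stands alone or replaces only criterion 3.
3. All others are unclassified.

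This gives each of the 36 profiles exactly one class: 28 inflammatory, 5 non-inflammatory and 3 unclassified if criterion 4 stands alone, or 28, 3 and 5 if it replaces only criterion 3. If Figure 1 already sets an order, write that order into the definitions instead.

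Report the numbers of patients who are discordant, unclassified, and excluded because of procedural risk. Add sensitivity ROCs on patients with measured specimens: (a) colonoscopy overrides a positive stool test when the two disagree; (b) unclassified patients are assigned all to one group, then all to the other. Whether specimens from patients excluded for risk are kept is not stated; those patients are counted, and enter (b) only if measured.

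The cost is some rewording and a few extra ROC runs. Measuring calprotectin at the end of the study leaves time to fix the rule first. The downside is a little more analysis and a possibly less favourable AUC. The rule governs research labels only; patient care does not change.

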## Data collection process

All patients are required to consent to the study. Their stool samples will be routinely sent for microscopic examination (cell count and parasites) and *C. difficile* toxin. Fecal calprotectin will be kept at -80 celsius degree and will be measured for fecal calprotectin at the end of study. The patients baseline characteristics, indication of hospitalization, treatment, and clinical progression will be obtained. All patients will be managed by primary physicians who do not know the results of fecal calprotectin level.

This protocol has been approved by Siriraj Institutional Review Board on January 24, 2019. The approval number is 718/2561(EC4).

## Outcome Measures

Primary outcome: To determine the efficacy of fecal calprotectin in distinguishing inflammatory nosocomial diarrhea from non-inflammatory nosocomial diarrhea.

Secondary outcome: Correlation of fecal calprotectin levels and prognosis of hospitalized patients with nosocomial diarrhea.

The participants with nosocomial diarrhea were tested for C.difficile and stool examination or further colonoscopy for definite diagnosis group of diarrhea. Their leftover specimens will be kept until the end of the study. Then all collected stool specimens will be measured for calprotectin levels. Overall data collected of 147 participants will be completed analyzed about August 2020.

### **Statistical Analyses**

The continuous data will be reported in mean and standard deviation or median and range as appropriate.

Categorical data will be reported in percentage or frequency.

Comparision of factors and patient characteristic between inflammatory and non-inflammatory diarrhea groups will be analyzed using independent t-test or Wilcoxon Rank Sum test for continuous variables, and chi-square test or fisher exact test for categorical variables.

Fecal calprotectin levels between inflammatory and non-inflammatory diarrhea will be shown in receiver operating characteristic curve(ROC). The best cut off will be calculated.

Correlation of fecal calprotectin levels and treatment outcomes, both univariate and multivariate analysis, will be analyzed by logistic regression.

P value < 0.05 will be considered statistically significant.

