## **Population**

### **1. Sample size**

In literature review, we found a study comparing fecal calprotectin levels between *C. difficile* associated diarrhea and antibiotic associated diarrhea. The median fecal calprotectin level in *C. difficile* associated diarrhea was 684.8 (range:203.7 to 1581.0) and the median level in antibiotic associated diarrhea was 66.5(range :23.1 to 145.7). Using Mann-Whitney U test with a standard normal of 1.96, alpha error of 5%, and power of 80%, the calculated sample size is 61patients in each group.

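### The best calprotectin cut-off is chosen and judged on the same patients with no correction, so its sensitivity and specificity will on average be overstated

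*Combined protocol and SAP*

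**What the plan says.** The Outcome Measures section defines the primary aim as "To determine the efficacy of fecal calprotectin in distinguishing inflammatory nosocomial diarrhea from non-inflammatory nosocomial diarrhea". For this aim the Statistical Analyses section plans an ROC curve comparing the two diagnostic groups and adds one sentence: "The best cut off will be calculated". It does not say what makes a cut-off best, and it fixes no threshold in advance.

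There is a single cohort. Specimens are frozen until the study ends, and "Then all collected stool specimens will be measured for calprotectin levels". On size, the Sample size section says "the calculated sample size is 61patients in each group" (122 in total), while Outcome Measures says "Overall data collected of 147 participants will be completed analyzed about August 2020". Limitations and Caveats says the groups are unequal but does not give the split.

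Neither the protocol nor the SAP text mentions a held-out sample, cross-validation, bootstrap, optimism correction or confidence interval. The limitations do not raise the matter. Reporting sensitivity and specificity at the cut-off is not stated in words. It is implied by an ROC curve with a best cut-off serving a diagnostic aim, and the Background describes accuracy in those terms.

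**The concern.** Picking the best of all observed cut-offs uses chance features of the sample as well as real separation. The same chance features then raise the sensitivity and specificity computed in that sample. The pair reported at the selected cut-off is therefore too high on average, and an ordinary binomial interval that treats the cut-off as fixed is too narrow.

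The Background presents calprotectin as a way to choose better which inpatients need colonoscopy. That is a decision made at a threshold, so the cut-off and its two accuracy figures are what a reader would carry into practice. As planned, the figures would flatter the test, and nothing would show how unstable the cut-off is.

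**Working it through.** **The plan's own figure.** The only computed design figure is 61 per group (Mann-Whitney, two-sided 5%, 80% power). No standard deviation is given, so it cannot be reproduced. With the difference in medians 684.8 − 66.5 = 618.3 and n = 2(1.96 + 0.84)²(SD/618.3)² per group, 61 requires a common SD of about 1219. By Noether's formula it requires P(X>Y) of about 0.65. This point does not depend on how 61 was derived; it is used below only as a group size.

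**Inputs.** From the documents: 61/61, and a total of 147 with an unknown unequal split. Assumed, because the documents do not give them: Youden's index as the meaning of best, normal distributions with equal variance (after transformation), AUC values from 0.60 to 0.986, and splits of 147 such as 30 inflammatory/117 non-inflammatory.

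**Method.** Non-inflammatory values are N(0,1) and inflammatory values N(δ,1), with δ = √2·Φ⁻¹(AUC). In each of 4,000 simulated studies per scenario:

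1. Choose the cut-off c that maximises in-sample J = sensitivity + specificity − 1.
2. Record the apparent sensitivity and specificity at c.
3. Compute the true values at that same c: sensitivity 1 − Φ(c − δ), specificity Φ(c).
4. Optimism = apparent J − true J.

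**Results** (sensitivity/specificity, %):

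| Split | AUC | Apparent | True at chosen cut-off | Optimism in J |
|---|---|---|---|---|
| 61/61 | 0.70 | 69.1/66.4 | 64.5/62.7 | 0.083 |
| 61/61 | 0.80 | 76.7/73.4 | 72.8/70.4 | 0.070 |
| 61/61 | 0.90 | 84.9/82.9 | 81.5/80.5 | 0.058 |
| 61/61 | 0.95 | 90.4/88.7 | 87.5/86.7 | 0.049 |
| 61/61 | 0.986 | 95.8/94.7 | 93.4/93.4 | 0.037 |
| 30/117 | 0.70 | 70.3/66.2 | 62.3/64.6 | 0.096 |
| 30/117 | 0.80 | 76.7/74.5 | 69.5/73.3 | 0.085 |
| 30/117 | 0.90 | 85.3/83.3 | 79.5/82.1 | 0.069 |

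At 61/61 and AUC 0.70, apparent J is 0.691 + 0.664 − 1 = 0.355 and true J is 0.645 + 0.627 − 1 = 0.272. The best J attainable by any cut-off in that model is 2 × 0.645 − 1 = 0.290, so the reported figure exceeds even the ideal one. Placing the cut-off midway between observations moves the true pair to 64.9/62.3; the sum is unchanged.

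At AUC 0.65 the optimism is 0.088 (61/61) and about 0.10 (30/117). Across all 24 scenarios the mean bias was upward, and apparent exceeded true in 82% to 94% of individual simulated studies.

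**Stability and intervals.** The chosen cut-off varies between studies with an SD of 0.25 to 0.48 within-group SDs. A naive 95% Wilson interval for sensitivity covered the true sensitivity at the chosen cut-off about 92%, 93%, 94% and 95% of the time at 61/61 for AUC 0.70, 0.80, 0.90 and 0.95. At 30/117 and AUC 0.70 coverage was 89%. The lowest figure in repeated runs was 87%.

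**Does the remedy work?** At 61/86 (total 147) and AUC 0.70, mean apparent J was 0.352, bootstrap-corrected 0.298 and true 0.271. The correction removes (0.352 − 0.298)/(0.352 − 0.271) = 0.054/0.081, about two thirds of the optimism.

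**The case against.** Several points on the other side are right. The plan names no Youden rule and no binomial interval, and it does not say outright that sensitivity and specificity will be reported; the sizes above rest on assumptions. The bias holds in expectation, not in every dataset. The AUC, a natural summary for the primary outcome, is untouched by the choice of cut-off.

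The strongest point is that the documents' own figures suggest good separation, where optimism is smaller. The Background cites 93% sensitivity and 96% specificity in outpatients. The two spreads in the Sample size section (203.7 to 1581.0 and 23.1 to 145.7) do not overlap if they are true ranges, and optimism at that separation would be near zero. Read as interquartile ranges under a log-normal model, they give an AUC of about 0.87. In addition, 2 to 4 points of bias per measure is small beside sampling error: 1.96·√(0.7 × 0.3/61) = 11.5 points at 70%, and 7.5 points at 90%. Finally, this is a first study in this setting, treating physicians do not see the result, and the bootstrap correction is only partial.

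These points limit the size of the problem but do not remove it. The cited figures come from other comparisons: outpatient bowel disease, and *C. difficile* against antibiotic-associated diarrhea. The inflammatory group here also admits patients on stool white cells or colonoscopic findings, so separation may well be weaker. At AUC 0.95 and 61/61 the overstatement is still about 0.05. Sampling error is random and an interval would show it, but none is planned. The selection bias has a known direction and goes unreported. A first study is also where later users are likely to take their threshold from.

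**Conclusion.** The concern holds. Followed as written, the plan gives upward-biased accuracy at the selected cut-off. With near-equal groups the average overstatement is about 1 to 5 points on each of sensitivity and specificity (J optimism 0.094 down to 0.037 at 61/61 as AUC rises from 0.60 to 0.986). With 30 inflammatory patients it reaches about 9 points on sensitivity at AUC 0.60 and about 8 at AUC 0.70. Under-coverage of a naive interval is modest with equal groups and good separation, and material when separation is weak and the inflammatory group small.

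These sizes assume a Youden rule and equal-variance normal distributions; the direction of the bias is secure, and the size depends on the true AUC and split. The AUC is not affected. This should be changed, but it does not invalidate the study.

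**What to change.** Amend the Statistical Analyses section to:

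- name the criterion that defines the best cut-off, for example the Youden index;
- repeat the whole cut-off search in at least 1,000 bootstrap resamples, and subtract from each apparent measure the mean of (value in the resample − value of that resample's cut-off in the original data);
- report apparent and optimism-corrected sensitivity and specificity, with bootstrap 95% intervals for AUC, cut-off, sensitivity and specificity;
- state that the cut-off needs external validation. This matters because the bootstrap left about a third of the optimism in the check above.

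The cost is a few lines of code and some SAP wording. No new patients or assays are needed. The reported accuracy will be slightly less favourable and the intervals somewhat wider.
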